- During the primary DISCOMS study, no evidence of recent new inflammatory disease activity (inactive by the Lublin criteria¹⁶). Pseudorelapses due to infection, fever, or other stressors as deemed by the local PI will NOT be excluded. Those who have already successfully completed the primary DISCOMS study without having a new relapse or MRI scan change, but who have a relapse or scan change AFTER ending participation in DISCOMS but before entering the extension ARE eligible and will be recruited, i.e. we do not wish to undercount new activity that occurs after exiting DISCOMS.
- Provides informed consent to continue in the extension trial.
- Willing to follow the protocol.

• Able to undergo a brain MRI without anesthesia, as part of routine care (i.e. paid for by their insurance). * Continuously will be defined as no less than 75% of all prescribed doses, with no time of greater than four weeks from last intended dose to have missed a dose (8 weeks for natalizumab, i.e. one missed dose).

Exclusion criteria:

- During original DISCOMS trial participant was randomized to the discontinue group, but then either restarted their DMT during the trial (study-defined 'treatment withdrawal), or wishes to restart their DMT after completing original DISCOMS study. Conversely, also excluded are those who completed the primary trial in the continue group and then discontinued, or wishes to discontinue, after completion of the primary study.
- Any MS relapse or new MRI scan lesion (3 mm or larger) during the primary DISCOMS trial, with relapse determined by the blinded examiner and MRI lesion determined by the blinded MRI reader.
- Significant (as defined by the PI) intolerance of presently-used DMT, if taking a DMT
- The following must **not** have occurred during the original DISCO MS study or since completing the study:
 - Use of any non-FDA-approved DMT
 - More than two courses of acute, systemic (IV or oral). Course is defined as three or more days continuously, and not to exceed 14 days. No use of chronic, systemic steroids, defined as 15 or more days. Any use of steroids to treat MS relapse, possible relapse, or pseudo-relapse is excluded. Inhaled or topical steroids for non-MS are not exclusionary.
 - Use of alemtuzumab, mitoxantrone, cyclophosphamide, methotrexate, cyclosporine, rituximab, or cladribine.
 - \circ $\,$ Use of any experimental agent used as a DMT for MS $\,$
 - Cancers other than basal cell skin cancers

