This will be a non-randomized, rater-blinded pragmatic trial, which is an extension of the randomized discontinuation trial (RDT)⁸², DISCOMS. While RDTs have been done in cancer^{83,84} and rheumatoid arthritis patients,⁶⁶ the original DISCOMS protocol was the first such study in MS. For this protocol, a subset of 100 subjects of the original 260 enrolled will be followed. Study sites will be limited to the top 10 recruiting sites across the United States from the DISCOMS study due to financial and cost-effectiveness issues. Those sites will have participants who have completed 18-24 months of the primary study. In practice, the vast majority, if not all, will have completed 24 months. We will explicitly include any who have completed, including those who already have exceeded 12 additional months after completion of the primary trial. Individuals who have successfully completed (retained original drug assignment and did not meet the primary endpoint of DISCOMS) the primary DISCOMS trial and are willing to retain their original drug assignment after completion and for an additional 12 months will be offered entry into the extension. The only exception to that will be individuals who continued the original drug assignment during and after the primary trial, up to 24 months, but who then had a relapse, new MRI lesion, or other MS-related reason between months 24 and 36 which resulted in their change of medication assignment. These individuals can and should be included, and counted as "failing" during the extension trial completing the Kaplan-Meier event free survival curve critical to the original hypothesis. A total of up to 100 patients will be consented and enter the extension trial, regardless of assignment, on a first come first serve basis to avoid selection biases to the extent possible. The intent is to take the first 100 who fulfill criteria and agree to participate. The plan is for a 50/50 distribution, but there may not be exactly 50 in each group. As of December 15, 2020, 123 had completed participation of the primary 24-month study, and information as to DMT use plans after finishing 2-years participation in DISCOMS was available for 84/123, 42 in each group (see Table 1 below). Notably, in the Discontinue group, 86% remained off DMT while only 60% in the Continue group plan to remain on a DMT (23/42 on the same DMT, two switching to an alternative). Overall 73% remained in the primary assignment grouping. If these ratios stay consistent as more finish DISCOMS, discontinuers will account for roughly 59% of the total enrolled in the extension trial. Also, of the 123 completers, 49 have also gone at least an additional 12 months since completion of DISCOMS, and they will be offered entry into the extension trial, should they otherwise fulfill criteria. There will be no placebo and no sham treatment. (Please see the statistics section the extension ns for power analyses discussions).

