
Table 1. Use of Disease Modifying Therapy after two years of participation in DISCOMS.

	Stop my DMT	17
Continue Discontinue	Continue my current DMT	23
	Switch to a new DMT	2
	Stay off my DMT	36
	Restart a prior DMT	5
	Restart a new DMT	1
	Total	84

The study procedures will be slightly different for those who are completing Month 24 of the primary trial and simply "rolling over" to extension on the same day, compared to those who already have completed the study. For those rolling over at Month 24, they will be offered participation in the extension trial. If they agree to participate, they will do a second study visit at the Month 24 visit, which concurrently will be Time Zero (T_0) for the extension. This will consist of obtaining informed consent and going through Inclusion/Exclusion criteria. All the data from Month 24 visit will comprise the baseline data for the extension. Current and past DISCOMS study participants will be identified and screened for eligibility. This may include individuals who already have surpassed a full year since last participation in the trial, so long as they continued their original group assignment after the completion of the primary study and for at least for one additional year, or until they had a relapse or new MRI lesion, as determined in screening. These individuals will explicitly be included, upon verification of the defining event. Patients will be approached at their next study visit or by phone (if they've already completed the original study) by the PI and/or a study coordinator about participating in the study. The local PI for the study will verify accuracy of meeting inclusion criteria, and screening and consent may take place in person or by electronic means. Participants must agree to have a single SOC, month 36 MRI done by their primary neurologist and have the results and the MRI disk sent to the study site, to be assessed by a blinded central reader as has been done during the primary trial. All research visits will be conducted at the same time as SOC visits when possible, or as separate visits if not possible or the patient receives SOC elsewhere. For those who have exceeded 30 months from onset in the primary trial, the P_1 visit (a telephone call) will not occur. All patients will undergo the T_1 visit at 36 months, or longer should they have already exceeded 36 months from onset of their participation in the primary trial.

Please see Table 2 below for the schedule of study activities.

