A thorough discussion of the trial, signing the informed consent form, and confirmation of inclusion/exclusion criteria will be completed during the baseline visit (T_0). Consenting may be done in-person on paper or using e-consent. If utilizing econsent, participants will be presented a consent form ahead of time, and upon signature in the REDCap system, participants will receive a pdf of what they 'signed' electronically via REDCap. A pdf will also be generated for study records. T₀ may occur on the same day as T₁ if the patient has already completed the main DISCOMS study and is within the window for the Month 36 visit. There will be one phone call (P1), conducted by the study coordinator, at 30 Months post-enrollment in the original DISCO MS trial. On this phone call, the participant will be asked about any new or ongoing adverse events, changes to medications, and any symptoms suggesting a potential relapse. If the participant joins the Extension study after they already passed 30 Months post-enrollment in the original DISCO MS trial, they will not do P₁. Those who have already exceeded 30 months since starting the primary DISCOMS trial will have the equivalent of the phone assessment at the T_0 visit. Participants will come in for 1 additional study visit; T_1 at 36 Months post-enrollment in the original DISCO MS trial. During T₁, patients will undergo a blinded EDSS exam and relapse assessment, vitals, complete an SDMT assessment, and will complete all PROs/comorbidities. All PROs/comorbidities may be completed on paper in person or remotely via the electronic platform within the visit window, based on site and patient needs. Participants will also undergo a standard of care MRI scan of the brain at T1, within 60 days before and 120 days after the study visit. Participants who have already exceeded 12 months from the end of the primary trial will still be recruited and simply do the T₁ visit at their earliest convenience. The maximum window will be 30 months after completion of the primary study, or 54 months since starting DISCOMS. Participants should always be brought in as close to 36 months as possible. Some participants' final study visit for the original DISCO MS study will be at 18 Months. For these subjects, the P₁ visit will occur 24 Months after enrollment in the original study, and T₁ will occur 30 Months after enrollment in the original study.

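### Eligibility texts conflict on people who changed medication after an MS event that followed DISCOMS, so sites could screen late events inconsistently while event-free time is counted to month 54

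*Combined protocol and SAP*

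**What the plan says.** **Texts that would turn such a person away**

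- III.B, inclusion criteria: discontinuers must have remained off DMT during and since DISCOMS, and continuers must have remained on it. A continuer may switch drug for intolerance, convenience or insurance reasons, but not because of new or worsening disease. No end date is given.
- III.B, exclusion criteria: continuers who stopped after completing DISCOMS are excluded, again with no end date and no allowance for MS events.
- III.C: people "willing to retain their original drug assignment after completion and for an additional 12 months will be offered entry into the extension". The sole stated exception is for those who had a "relapse, new MRI lesion, or other MS-related reason between months 24 and 36 which resulted in their change of medication assignment". They are to be counted as failures.

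**Texts that would admit the same person**

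- III.B, inclusion criteria: those "who have a relapse or scan change AFTER ending participation in DISCOMS but before entering the extension ARE eligible and will be recruited". No month limit is set, and the stated reason is to avoid undercounting new activity.
- III.C, on recruiting people more than a year past DISCOMS: they qualify if they kept their assignment "for at least for one additional year, or until they had a relapse or new MRI lesion, as determined in screening". The text adds: "These individuals will explicitly be included, upon verification of the defining event".

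**Period counted**

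- III.C: "The maximum window will be 30 months after completion of the primary study, or 54 months since starting DISCOMS". Table 2 gives the matching T1 window of month 36, minus 1 to plus 18 months.
- III.F, Aim #1: Kaplan-Meier estimates, with each person counted at the event time or censored at last known status, and the 0.08 margin examined at later follow-up times.

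**The concern.** Take two people first contacted at month 45. One is event-free. The other relapsed at month 40 and then changed medication. The first can enrol, with event-free time counted to month 45. Whether the second can enrol depends on which paragraph the site applies.

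If the second is refused, event-free time after month 36 enters the curve while some of the events from the same months do not. That is selection at entry, tied to the outcome. The analysis cannot repair it, because the refused person contributes no data. It would bear on the part of the curve that the extension exists to supply, and it would work against the protocol's own aim of not undercounting activity after DISCOMS.

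The exception window also fits poorly for people who finished DISCOMS at 18 months. Their T1 is at month 30, so an event with a medication change at month 20 precedes the window. III.C expects few such people, so this is secondary.

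**Working it through.** **1. The plan's own figures.** No stated sample size, power or error rate depends on the 24-36 window. The one inferential figure (III.F, Sample Size) reproduces: 10/50 v 3/50 by Fisher's exact test gives a one-sided p = 0.0357, stated as 0.036. For scale, 9/50 v 3/50 gives p = 0.061, so one event matters at this size. A lost continue-arm event would move p the other way.

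**2. Windows.** The exception covers 36 - 24 = 12 months. Follow-up after month 24 can last 54 - 24 = 30 months. So 30 - 12 = 18 months lie outside the exception.

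**3. The month-40 medication changer under each text**

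| Text | Result |
|---|---|
| III.B inclusion, discontinuer who restarted | not met |
| III.B inclusion, continuer who switched for disease activity | not met |
| III.B exclusion, continuer who stopped | excluded |
| III.C sole exception | does not apply (month 40) |
| III.C 12-month retention rule | met (kept to about month 36) |
| III.B inclusion, post-DISCOMS events | eligible; silent on medication change |
| III.C recruitment of people past one year | included once the event is verified |

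**4. Who is exposed.** People first screened after month 36. At 15 December 2020, 49 of 123 completers (39.8%) were at least 12 months past DISCOMS (III.C).

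**5. Size on the strict reading.** The documents do not give the inputs needed, so this is an illustration. Assumptions:
- constant hazard from month 24, h = -ln(1 - p)/12 per month, where p is the yearly event proportion;
- 39.8% are enrolled and assessed at a time uniform over months 36-54, and the rest end at month 36;
- q is the share of events after month 36 but before enrolment that led to a medication change and hence refusal.

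On the inclusive reading the 48-month proportion is 1 - (1 - p)². For p = 6% this is 1 - 0.94² = 11.6%. The strict-reading values come from a Kaplan-Meier simulation of 400,000 people per scenario. Direct numerical integration of the same model agrees to about 0.1 point.

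| p per year | Inclusive | Strict, q = 0.25 | q = 0.5 | q = 1 | Refused per 100 |
|---|---|---|---|---|---|
| 3% | 5.9% | 5.2% | 4.4% | 3.0% | 0.2-0.9 |
| 6% | 11.6% | 10.2% | 9.0% | 6.1% | 0.4-1.7 |
| 20% | 36% | 33% | 29% | 21% | 1.2-4.8 |

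At 6% the shortfall runs from 11.6 - 10.2 = 1.4 to 11.6 - 6.1 = 5.5 points. At 3% it runs from 0.7 to 2.9 points.

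**6. Between-arm difference.** If a fraction f of events is refused, the proportion seen is p(1 - f)/(1 - pf). Assume 8% v 4% per year (discontinue v continue) over 9 months: 1 - exp(-0.06) = 5.8% v 1 - exp(-0.03) = 3.0%, a true difference of +2.9 points.

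| f, discontinue / continue | Difference seen |
|---|---|
| 0.8 / 0.4 | 1.2% - 1.8% = -0.6 |
| 0.6 / 0.6 | 2.4% - 1.2% = +1.2 |
| 0.2 / 0.8 | 4.7% - 0.6% = +4.1 |

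The error can go either way, and the documents give no value for f in either arm.

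**The case against.** The strongest reply is that the exception has been misread. The rule it modifies asks for 12 further months in the assigned group, to about month 36, and the 24-36 window matches that. Someone who changed medication at month 40 kept the assignment for the required year and needs no exception. The recruitment text in III.C then includes such people in terms, and III.B admits post-DISCOMS events without a limit.

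This stands, and it defeats a reading that a reader might infer: that late events leading to a medication change are definitely screened out. The documents do not say that. The reply does not remove the conflict, because the open-ended III.B criteria remain, and III.C has the local investigator verify the inclusion criteria. Even there the wording is uneven: the discontinue-arm exclusion names those who restarted during the trial or wish to restart, and does not clearly reach someone who has already restarted after a later event. The inclusion criterion does reach that person.

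Three limits on impact also stand. Events after month 36 without a medication change are eligible on either reading. Lesions first seen on the T1 MRI are found after enrolment. People enrolled before their event are unaffected.

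Finally, III.E concedes insufficient power for non-inferiority, and III.F puts estimation first. That lowers the weight on the 0.08 rule, but a biased late curve is a problem for estimation too.

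**Conclusion.** The contradiction is real and should be resolved. It is a possible entry-selection bias that depends on how sites read the criteria, and it is not a demonstrated one. On the strict reading, each arm's curve after month 36 is too low, by about 1.4 to 5.5 points at month 48 under an assumed 6% per year. On the inclusive reading the bias is zero. The range rests on the assumed hazard, the assumed enrolment pattern and the unknown share of events that led to a medication change. Few people would be refused (about 0.4 to 1.7 per 100 at 6% per year), but few events are expected.

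A reader might also infer that the bias favours non-inferiority, since any restart in the discontinue arm is a departure from assignment. The documents do not support a direction. III.B also bars continue-arm switches made for disease activity, and III.D refers people in both arms who reach an endpoint back to their neurologist to consider restarting or switching. The net effect depends on arm-specific rates of medication change that are not given.

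**What to change.** Put one identical statement into the III.B inclusion criteria, the III.B exclusion criteria and both places in III.C. It should say that a person who kept the assignment until a relapse or new MRI lesion, occurring between exit from DISCOMS (month 18 to 24) and T1, up to the end of the T1 window, stays eligible and is counted as an event, even if medication then changed. The period in which an event preserves eligibility then equals the period in which event-free time is counted, and 18-month completers are covered. The present exception also names other MS-related reasons. The statement should say whether these preserve eligibility and count as events, since the primary endpoint in III.D has only relapse and lesion.

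Reconcile one further text at the same time. III.B excludes anyone given steroids for an MS relapse since completing DISCOMS, whereas III.C and III.D count steroid-treated MS symptoms as a Protocol defined relapse. Unless these are reconciled, some late events could still be refused at entry.

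If the month-36 limit is kept instead, censor every participant at month 36 in Aim 1 and make no claim beyond it.

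The cost is wording in the protocol and the screening form. A few more people with events would become eligible within the cap of 100.

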Sample Size: The sample size was driven by budget considerations and the expected number who could complete the extension within a reasonable time period. We chose to focus on those who have been maintained in their assigned treatment arms from the original randomization to allow extension of time to event analyses. We considered including those who would go back on therapy or who subsequently stopped therapy, but felt that not only would the numbers likely be smaller than desired, they would diminish the available slots for the most informative participants (those maintaining their randomized assignment). Thus, while we expect roughly equal numbers from both treatment arms (the alternative hypothesis originally posed, that the two treatments are equal), we will have approximately 50 participants per arm. If we assume that there are 50 participants in each arm and 20% of the discontinue arm fails compared to 6% (10 and 3 of each group respectively), a fisher's exact test would yield a one sided p-value of 0.036, sufficient to say the discontinue group has done worse. We also plan to test for baseline differences between the two groups, using data from the original RCT, and will adjust for any significant baseline differences.

It may be that there are differences between those with relapsing forms vs progressive forms of MS after discontinuation of their DMT. While we will not be powered to assess differences separately by relapsing or progressive forms, we have a pre-planned descriptive analyses for this important question, as well as other subgroup analyses. These will include analysis based on sex, age, disease duration, time since last relapse, specific DMT, and others since study outcomes will not be powered for stratification by MS type or heterogeneity of treatment effects, they will be simply examined as estimates of longer term treatment follow-up.

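### Entry after a post-DISCOMS treatment change depends on the outcome, so event-free time is lost and event risk is inflated; the direction of the between-arm bias is unknown

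*Combined protocol and SAP*

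**What the plan says.** Section III.B limits entry to people who stayed in their assigned group during and after DISCOMS. Its exclusion criteria remove discontinuers who restarted during the trial or wish to restart afterwards, and on the other side "also excluded are those who completed the primary trial in the continue group and then discontinued, or wishes to discontinue".

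Section III.C makes one exception, for people who kept their assignment through the primary trial and then "had a relapse, new MRI lesion, or other MS-related reason between months 24 and 36 which resulted in their change of medication assignment". They are to be included and counted as failing on the Kaplan-Meier curve. The text after Table 1 applies the same idea to people already more than a year past DISCOMS: they must have kept their assignment for at least that year, "or until they had a relapse or new MRI lesion, as determined in screening". Section III.B gives the motive, saying that people with activity between DISCOMS exit and entry "ARE eligible and will be recruited, i.e. we do not wish to undercount new activity that occurs after exiting DISCOMS".

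The analysis plan for Aim 1 (III.F) counts a protocol-defined relapse or a new brain lesion, and otherwise censors at last known status. It sets a non-inferiority rule: the upper 95% limit for the difference must lie below 0.08. The Sample Size text explains why people who changed treatment are left out: "they would diminish the available slots for the most informative participants".

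**The concern.** Take two completers who stay on assignment for the same number of months after DISCOMS and then change treatment before they are approached. One changed because of a relapse or new lesion and the other had no event. The first enters the curve as a failure. The second never enters, and neither do the months that person spent event-free on assignment. The plan protects the numerator against undercounting but not the denominator.

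The censoring rule for Aim 1 does not help, because it applies only to people who were admitted. First-come enrolment does not help either, since the selection happens at eligibility. The Sample Size argument about slots explains why changers get no T1 visit. It does not explain why their time at risk before the change should be dropped.

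At stake are the estimated event risk in each arm and, if event-free changing or true risk differs between arms, the difference to be compared with the 0.08 margin.

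**Working it through.** **Who is affected.** Only people whose change fell after DISCOMS exit and before enrolment.
- Month-24 rollovers are enrolled before any later change, so they are not affected.
- People who changed at exit are out whatever happened next, so they add no bias.
- Changes after enrolment do not remove a person. III.D follows participants to the end after the primary results are disclosed, and also after an endpoint.
- The exposed group may not be small. III.C reports 123 completers by December 2020, 49 of them at least 12 months past DISCOMS, and T0 may fall on the same day as T1.

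**The plan's own figures.** From Table 1, 17 of 42 continuers (40.5%) planned to stop and 6 of 42 discontinuers (14.3%) planned to restart. Staying on assignment is 25/42 = 59.5% and 36/42 = 85.7%, overall 61/84 = 72.6%, and discontinuers are 36/61 = 59.0% of stayers. These match the stated 60%, 86%, 73% and 59%. The one-sided Fisher p-value for 10/50 v 3/50 is 0.0357, matching the stated 0.036.

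**Model (my assumptions).** Let p be the true 12-month event risk and s the share that would change treatment over those 12 months, both at constant and independent rates: λ = -ln(1-p), μ = -ln(1-s). All follow-up precedes enrolment. Only events before a change are kept, and event-free changers are dropped.
- P(neither) = (1-p)(1-s)
- P(event first) = λ/(λ+μ) × [1 - P(neither)]
- Observed risk = P(event first) / [P(event first) + P(neither)]

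Worked case, p = 6%, λ = 0.0619:
- Continue, s = 40.5%: μ = 0.5188, P(neither) = 0.5595, P(event first) = 0.0469. Observed risk = 0.0469/0.6065 = 7.7%.
- Discontinue, s = 14.3%: μ = 0.1542, P(neither) = 0.8057, P(event first) = 0.0556. Observed risk = 0.0556/0.8614 = 6.5%.

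With Table 1 shares standing in for later changes:

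| True risk, both arms | Continue observed | Discontinue observed | Difference (true value 0) |
|---|---|---|---|
| 5% | 6.5% | 5.4% | -1.1 points |
| 6% | 7.7% | 6.5% | -1.3 points |
| 10% | 12.8% | 10.7% | -2.0 points |

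A looser reading also keeps events that follow the change: observed risk = p/[p + (1-p)(1-s)]. It gives -2.8 points at 6% and -4.2 at 10%. The text after Table 1, which requires assignment to be kept until the event, does not support that reading, so these are upper bounds.

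**How far the sign depends on the inputs.**
- No changes between exit and enrolment: bias 0.
- Equal s of 27.4% (23/84) in both arms, true risks 6% v 14%: observed 7.0% v 16.1%, a bias of +1.1 points, against non-inferiority.
- A simpler version with changes spread evenly over the year, p(1-w/2)/[p(1-w/2) + (1-p)(1-w)], where w is the share changing event-free: at p = 10%, w of 10% continue v 14% discontinue gives +0.2 points, and 40% v 5% gives -2.7.

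**Timing of detection.** The only scheduled scan is at T1. A person censored before T1 is not in the risk set there, so dropping that person does not change that step. If half of the event hazard falls at T1 (an assumption; the documents give no split), the model is applied only to the first half and the bias becomes about -0.5 points at 5% and -1.0 at 10%. If all events are found at T1, it is 0.

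**Effect on the 0.08 rule.** With 50 per arm, Newcombe limits and true risks at the margin (6% v 14%), the chance of wrongly meeting the rule rises from 2.2% to 3.1% under the model above with Table 1 shares.

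**The failure definition.** III.C counts as failing a person admitted for "or other MS-related reason between months 24 and 36 which resulted in their change of medication assignment". III.D and the Aim 1 analysis recognise only a protocol-defined relapse or a new or enlarging brain lesion. The two cannot both hold.

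**The case against.** A reader might infer that the rule inflates the continue arm most and so favours non-inferiority, because 40% of continuers planned to stop and only 14% of discontinuers planned to restart. The documents do not support that. Table 1 records intentions at DISCOMS exit, and people who changed then add no bias. Continuers who remain after that exclusion are those who chose to stay, and nothing shows how often they changed later compared with discontinuers. The clause on other MS-related reasons could push the other way, if restarts driven by symptoms are commoner off treatment.

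The effect is also bounded. It needs a change before enrolment and an event dated before T1, so applying the shares to a whole arm overstates it. III.E concedes that the extension is underpowered for non-inferiority, and Aim 1 makes estimation the primary goal. With 50 per arm the 95% half-width is 1.96 × √[2p(1-p)/50], which is 8.5 points at 5% risk and 11.8 at 10%, well above the modelled bias.

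These points remove any claim about direction and limit the size. They do not remove the defect. The rule distorts the estimates that the plan calls its main goal, the 0.08 rule is still stated, and no text handles the lost time at risk.

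**Conclusion.** For people entering after DISCOMS exit, admission following a treatment change depends on whether they had an event. This biases the event risk upward in any arm with event-free changes before enrolment. The direction of the bias in the between-arm difference is unknown. With Table 1 shares as a stand-in, constant and independent rates, and equal true risk of 5% to 10%, it is about -1 to -2 points against the 8-point margin, and less if many events surface on the T1 scan. Equal rates of change with a higher true risk in the discontinue arm would reverse the sign.

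The contradiction over other MS-related reasons is separate and needs no modelling. This should be corrected, but it does not by itself invalidate the extension.

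**What to change.** 1. Count as failures only verified protocol-defined relapses and new or enlarging brain lesions. Reconcile the entry criteria in III.B, the exception and late-entrant text in III.C, and the endpoint in III.D and III.F. The III.B exclusion for steroid treatment of relapse since DISCOMS also has to be reconciled with the stated wish to recruit people who relapsed in that period.
2. Let DISCOMS completers at the ten sites who had no endpoint event, and who changed assignment after exit and before enrolment, contribute time from exit to the change date and be censored there. Take the change date, relapse history and any existing scan at the screening contact already planned. No T1 visit or enrolment slot is used. If changing is unrelated to event risk, the model bias above becomes 0.
3. Report a sensitivity analysis without those admitted through the exception.

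The cost is a short screening form with consent, a censoring rule and slightly more site work. The drawback is weaker ascertainment in the added people: no blinded examination within 7 days of symptoms and possibly no scan before the change. Some events will be missed, which could bias the other way, so results should be shown with and without them.
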